9.1.7 Visit 7: Day 180 – Follow Up

1. Vital signs (heart rate, blood pressure, temperature) and weight will be measured
2. Blood glucose and current HbA1c will be measured
3. A blood sample will be drawn for asservation
4. Patients of both study groups will fill out the SIMPAQ- and SF-36 questionnaire to evaluate quality of life and daily physical activity compared to baseline
5. Anti-diabetic medication of the patient will be assessed through questioning
6. Re-hospitalizations and unplanned physician consultations will be assessed through

questioning

7. Patients who participated in the intervention group will be questioned about current physical activity levels and if they maintained the intense lifestyle intervention during the 3 months without weekly phone calls and further support by the study team
8. Actigraph readout will be done

9.1.8 Visit 8: 1 Year – Telephone Follow Up

Telephone follow-up visit with the general practitioner, treating endocrinologist or participant to inquire about HbA1c, weight and medication one year after study enrollment. This visit will be held for both groups.

10. SAFETY

During the entire duration of the study, all serious adverse events (SAEs) are collected, fully investigated and documented in source documents and case report forms (CRF). Study duration encompasses the time from when the participant signs the informed consent until the last protocol-specific procedure has been completed, including a safety follow-up period.

10.1.1 Definition and Assessment of (Serious) Adverse Events and Other Safety Related Events

An **adverse event (AE)** is any untoward medical occurrence in a patient or a clinical investigation participant administered a pharmaceutical product and which does not necessarily have a causal relationship with the study procedure. An AE can therefore be any unfavourable and unintended sign (including an abnormal laboratory finding), symptom, or disease temporally associated with the use of a medicinal (investigational) product, whether or not related to the medicinal (investigational) product. [ICH E6 1.2]

A **serious adverse event (SAE)** is classified as any untoward medical occurrence that:

- results in death,
- is life-threatening,
- requires in-patient hospitalization or prolongation of existing hospitalization,
- results in persistent or significant disability/incapacity, or
- is a congenital anomaly/birth defect.

In addition, important medical events that may not be immediately life-threatening or result in death, or require hospitalization, but may jeopardize the patient or may require intervention to prevent one of the other outcomes listed above should also usually be considered serious. [ICH E2A]

SAEs should be followed until resolution or stabilization. Participants with ongoing SAEs at study termination (including safety visit) will be further followed up until recovery or until stabilization of the disease after termination.

Assessment of Causality

Both investigator and sponsor-investigator make a causality assessment of the event to the study drug, based on the criteria listed in the ICH E2A guidelines:

Relationship	Description
Definitely	Temporal relationship Improvement after dechallenge* Recurrence after rechallenge (or other proof of drug cause)
Probably	Temporal relationship Improvement after dechallenge No other cause evident
Possibly	Temporal relationship Other cause possible
Unlikely	Any assessable reaction that does not fulfil the above conditions
Not related	Causal relationship can be ruled out

*Improvement after dechallenge only taken into consideration, if applicable to reaction

Suspected Unexpected Serious Adverse Reactions (SUSARs)

The sponsor-investigator evaluates any SAE that has been reported regarding seriousness, causality and expectedness. If the event is related to the investigational product and is both serious and unexpected, it is classified as a SUSAR.

Assessment of Severity

The grades for severity described in the Common Terminology Criteria for Adverse Events (CTCAE, Version 5.0) are used.

10.1.2 Reporting of SAEs and Other Safety Related Events

Reporting of SAEs

All SAEs must be reported immediately and within a maximum of 24 hours to the sponsor-investigator of the study. The sponsor-investigator will re-evaluate the SAE and return the form to the site.

If it cannot be excluded that the SAE is attributable to the intervention under investigation, the Investigator reports it to the EC via BASEC within 15 days. If the SAE occurs at one of the study sites, the coordinating investigator reports the events to the CEC within 15 days. The other ECs involved in the trial receive SAEs resulting in death in Switzerland via sponsor-investigator via BASEC within 7 days.

Exemptions from expedited reporting may be possible if the SAE is either a clear result of the underlying disease or well-known and described in the currently approved product information (mainly for phase IV studies). Please define those SAEs that are exempted from expedited reporting.

Reporting of SUSARs

A SUSAR needs to be reported to the EC (local event via local investigator) via BASEC and to Swissmedic for category B and C studies (via sponsor-investigator) within 7 days, if the event is fatal, or within 15 days (all other events).

The sponsor-investigator must inform all investigators participating in the clinical study of the occurrence of a SUSAR. All ECs involved in the trial will be informed about SUSARs in Switzerland via sponsor-investigator via BASEC according to the same timelines.

Reporting of Safety Signals

All suspected new risks and relevant new aspects of known AEs that require safety-related measures, i.e. so called safety signals, must be reported to the sponsor-investigator within 24 hours. The sponsor-investigator must report the safety signals within 7 days to the EC (local event via local investigator) via BASEC and to Swissmedic in case of a category B or C study.

The sponsor-investigator must immediately inform all participating investigators about all safety signals. The other ECs involved in the trial will be informed about safety signals in Switzerland via the sponsor-investigator.

Reporting and Handling of Pregnancies

Pregnant participants must immediately be withdrawn from the clinical study and substituted as gestational diabetes patients require a stricter blood glucose management and more likely an insulin therapy and therefore meet our exclusion criteria. Any pregnancy during the treatment phase of the study and within 30 days after discontinuation of the intervention will be reported to the sponsor-investigator within 24 hours. The course and outcome of the pregnancy should be followed up carefully, and any abnormal outcome regarding the mother or the child should be documented and reported.

Periodic reporting of safety

An ASR is submitted once a year to the local EC via local investigator from all sites. The sponsor-investigator prepares it, and then submits it to the participating investigators. The participating investigators submit it to the local committees.

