We believe it is crucial to stress the importance of lasting lifestyle changes for metabolic control from the very point of diagnosis. Intervention early in the course of the disease often suffices to control metabolic dysregulation and may even have a durable impact. However, as mentioned above, multiple reasons including non-compliance as well as doubt about the efficacy of sport and diet changes compared to drugs make a lasting change in lifestyle difficult. Furthermore, most patients with type 2 diabetes remain asymptomatic for a prolonged period of time, leaving patients in doubt about the immediate benefit of lifestyle changes. Often, untreated type 2 diabetes manifests itself for the first time with symptoms of polyuria and polydipsia. This offers a unique opportunity to demonstrate the potential of lifestyle changes. However, in daily practice, symptomatic patients with polyuria and polydipsia are typically referred to an emergency room and are treated with drugs and hospitalized. With this study, we therefore aim to implement lifestyle intervention as first line treatment in new onset type 2 diabetes patients. We expect to achieve a durable educational impact with this approach and to increase the patients' motivation for glycemic control through healthy lifestyle while keeping pharmacological aids at a minimum.

Investigational Product (Treatment, Device) and Indication

No investigational products are used in this trial.

Preclinical Evidence

Not applicable.

Clinical Evidence to Date

Refer background and rationale.

Explanation for Choice of Comparator (or Placebo)

The control treatment used in this trial is based on the current standard of care for diabetes according to national and international guidelines (American Diabetes 2012). There is no medical disadvantage for the participants of the control group.

Risks/Benefits

Subjects will only be performing the bicycle exercise when they are found to be eligible by the responsible medical doctor with concern to their clinical status. During the remaining study period patients are encouraged to be physically active. This may increase the risk for physical activity associated accidents (i.e. adverse events) but does not represent a greater risk within the study compared to general physical activity in the normal population.

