7. STUDY POPULATION

Eligibility Criteria

Participants fulfilling all of the following inclusion criteria are eligible for the study

- Able to give informed consent as documented by signature (Appendix ICF)
- Type 2 diabetes diagnosed within the last two years according to the ADA-criteria
- Age \geq 18 years
- HbA1c \geq 7.5 %

The presence of any one of the following exclusion criteria will lead to exclusion of the participant:

- Clinically unstable patient as defined by the physicians on duty e. g. signs of new ischemia in the ECG, systolic blood pressure \geq 200 mmHg, fever \geq 38.5 °C, symptoms of SIRS or reduced vigilance.
- Anti-diabetic medication for \geq 24 hours
- Inability to perform a bicycle exercise during 30 minutes
- Previous lifestyle intervention by an endocrinologist
- Engagement in physical activity more than five times per week
- Enrollment in other interventional study

Recruitment and Screening

Patients are recruited after seeking medical consultation at the emergency room, medical outpatient clinic of the respective study centers or their general practitioners. Patients will be assessed and enrolled in the study by the study team.

Assignment to Study Groups

Patients are randomized to the intervention or the control arm using a computer-generated number after agreeing to participate in the study.

Criteria for Withdrawal/Discontinuation of Participants

Participants may withdraw or be withdrawn at any time. Subjects who discontinue participation may be replaced. Reasons for discontinuation are:

- Participant withdraws informed consent
- Participant does not comply with study treatment or the concomitant procedures. Non-compliance for this study is defined as completion of less than 50% of the training program during two weeks
- Pregnancy
- Participant is no longer willing to continue the study because of any reason
- The incidence or severity of adverse events (AEs) indicate a potential health hazard to the participant

Withdrawal will be documented in the database with all other study data.

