9.1.5 Visit 1: Day 0 – Initial Consultation

All Patients will be recruited at the ER department or outpatient clinic of a participating study center or by their personal practitioner after presenting with a newly diagnosed or untreated type 2 diabetes mellitus. The treating physician will assess whether the patient is clinically fit to participate in the study and will order an ECG if necessary.

If the patient meets all of the inclusion and none of the exclusion criteria, he or she is required to sign the ICF. The patient will then be randomized 1:1 to the intervention or the control group.

Medical history is taken followed by a physical examination and drawing of blood samples for a venous blood gas analysis (pH, pCO₂, base excess, bicarbonate, glucose) and a baseline HbA1c (may be up to 14 days old).

Patients allocated to the intervention group will then perform a 30-minute bicycle exercise at 60 % of the age-adjusted maximal heart rate. Blood samples will again be drawn at the end of the exercise as well as 30 and 90 minutes after its completion to determine blood glucose levels and to do a venous BGA at 90 minutes after the bicycle exercise.

All participants of the intervention group will receive a structured plan for an intensive lifestyle intervention for the following 3 months as well as an actigraph provided by the DSBG to monitor daily physical activity between study visits.

Patients allocated to the control group will receive the standard diabetes care practiced at the study center according to national and international guidelines.

Patients will be discharged when clinically stable and no comorbidities require further hospitalization.

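### The pregnancy rule in Section 10.1.2 relies on an exclusion criterion that does not exist: none of the six exclusions names pregnancy

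*Protocol*

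**What the plan says.** Section 10.1.2, under Reporting and Handling of Pregnancies, states: "Pregnant participants must immediately be withdrawn from the clinical study". The reason given is that patients with gestational diabetes need tighter glucose management and are "more likely an insulin therapy and therefore meet our exclusion criteria".

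The exclusion list is in Section 7 and again in the synopsis, with the same six items. The one that bears on insulin reads "Anti-diabetic medication for \geq 24 hours". The inclusion criterion on diagnosis reads "Type 2 diabetes diagnosed within the last two years according to the ADA-criteria". Pregnancy does appear in Section 7, but only among the five reasons for discontinuing a participant already in the study.

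Section 9.1.5 (Visit 1) sets the order of events: "If the patient meets all of the inclusion and none of the exclusion criteria, he or she is required to sign the ICF". Randomisation 1:1 comes next, and after the baseline assessments "Patients allocated to the intervention group will then perform a 30-minute bicycle exercise".

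**The concern.** Section 10.1.2 tells the reader that pregnant patients are already excluded, and the list that sites screen against does not exclude them. If that list is applied literally, the protocol admits a patient whom it must remove immediately.

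Three things follow: an avoidable enrolment, an avoidable withdrawal after randomisation, and, in the intervention arm, possible exposure to the day-0 bicycle exercise, because that exercise follows randomisation in the same visit.

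The sponsor's own reasoning shows why she should not enter. It says that pregnancy calls for stricter glucose control and makes insulin more likely. Section 8 bars insulin in the intervention arm except as rescue medication. It requires therapy to be reassessed when glucose stays above 15 mmol/l for more than 7 consecutive days, or on symptomatic hyperglycaemia or re-hospitalisation.

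**Working it through.** The point rests on comparing sections of the text; the protocol gives no figure to reproduce.

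**Step 1: test the claim in Section 10.1.2 against each exclusion criterion (Section 7; same six in the synopsis).**

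| Exclusion criterion | Names pregnancy? | Met by a stable, unmedicated pregnant woman? |
|---|---|---|
| Clinical instability as judged by the duty physicians | No; not among the examples | No, unless the physician so judges |
| Anti-diabetic medication for 24 hours or more | No | No; it concerns treatment taken, not treatment likely to be needed |
| Unable to cycle for 30 minutes | No | Not necessarily |
| Earlier lifestyle intervention by an endocrinologist | No | Not necessarily |
| Physically active more than five times per week | No | Not necessarily |
| In another interventional study | No | Not necessarily |

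Criteria naming pregnancy: 0 of 6. Discontinuation reasons naming pregnancy (Section 7): 1 of 5.

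**Step 2: see whom the stated reason covers.** The reason speaks of gestational diabetes. A patient with gestational diabetes alone does not have type 2 diabetes, so an inclusion criterion already keeps her out. The reason therefore does nothing for a pregnant woman whose diagnosis is type 2 diabetes.

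**Step 3: follow that woman through the protocol.** Suppose she is an adult known to be pregnant, with type 2 diabetes diagnosed within two years, HbA1c of at least 7.5%, no anti-diabetic medication, clinically stable, able to cycle for 30 minutes, and with none of the last three exclusions.

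1. Section 7: all inclusion criteria met, no exclusion criterion met.
2. Section 9.1.5: she may sign consent and be randomised.
3. Section 6.1.1: allocation is 1:1, so the chance of the intervention arm is 1/2.
4. Section 9.1.5: in that arm she goes on to the bicycle exercise.
5. Section 10.1.2: she must be withdrawn immediately.

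**Step 4: size the consequence.** If Section 10.1.2 is obeyed, exposure is at most one session: 30 minutes of cycling within a procedure of about two hours (Section 6). The protocol gives no age or sex distribution, so the number of such patients cannot be derived. The planned size is unaffected: 28 × 2 = 56 evaluable patients and 62 enrolled, which leaves 62 − 56 = 6 for loss to follow-up. One such patient would use one of those six at most, and only if her primary endpoint were missing.

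**The case against.** The strongest reply has four parts.

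- **The cross-reference is loose, not empty.** Section 10.1.2 argues through insulin, which points to the medication exclusion, and it speaks of participants already enrolled. For someone who becomes pregnant on study and starts insulin, the link can be understood. This is a fair reading of what was meant, but a likely need for insulin does not satisfy a criterion about medication taken for at least 24 hours, and the sentence says that the criteria are met.

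- **No sensible site would enrol her.** Pregnancy is listed as a discontinuation reason just below the exclusions, and Section 10.1.2 makes the intent plain. Section 9.1.5 also provides that "The treating physician will assess whether the patient is clinically fit to participate in the study", and Section 3 (Risks/Benefits) says "Subjects will only be performing the bicycle exercise when they are found to be eligible by the responsible medical doctor". The instability criterion is open-ended as well. All of this makes the path unlikely. None of these checks names pregnancy, however, and the check in Section 3 depends on eligibility, which is where the criterion is missing.

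- **Harm is not shown.** The exposure is one supervised session at 60% of calculated maximum heart rate, and nothing in the protocol says that this is dangerous in pregnancy. Immediate withdrawal also removes the larger worry, three months without glucose-lowering drugs. This stands, and it limits the weight of the point.

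- **The remedy reaches only known pregnancies.** This also stands. An unrecognised pregnancy at entry would still be enrolled and would fall under the existing discontinuation rule.

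**Conclusion.** The concern holds. Section 10.1.2 states that pregnant patients meet the exclusion criteria, and they do not: 0 of 6 criteria name pregnancy, and the only insulin-related item covers past treatment. A woman known to be pregnant, with unmedicated and stable type 2 diabetes, is eligible as written and must be withdrawn as soon as she is enrolled.

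The point is minor. It assumes that a site applies the exclusion list literally and that the physician's discretionary checks do not stop her. Few or no patients are likely to meet that path. The worst outcome under the protocol as written is one bicycle session followed by a forced withdrawal after randomisation. The planned sample size, power and analysis method are not affected. The rule for pregnancies that begin during the study is consistent between Sections 7 and 10.1.2 and needs no change.

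**What to change.** - Add pregnancy as a seventh exclusion criterion in Section 7 and in the synopsis.
- Reword the first sentence of the pregnancy text in Section 10.1.2. For example: participants who become pregnant are withdrawn because pregnancy is an exclusion criterion and requires stricter glucose management. It should no longer infer exclusion from a likely need for insulin.
- Keep pregnancy as a discontinuation reason for pregnancies that begin on study.

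The cost is one line in each of two lists and one rewritten sentence. Visits, sample size and analysis stay as they are.

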10.1.3 Follow Up of (S)AEs

All subjects who experience AEs will be followed until the event resolves or until the subject's participation in the study ends. For those AEs judged to be unrelated to the study intervention, the outcome at last observation will be recorded on the appropriate pages of the CRF.

Subjects experiencing AEs that were judged to be possibly, probably, or definitely related to a study

intervention will be followed until the events resolve or until the event is judged to be chronic or stable. Resolution of such events will be documented on the appropriate pages of the CRF.

11. STATISTICAL METHODS

Hypothesis

We hypothesize that lifestyle intervention lowers HbA1c effectively without antidiabetic drugs. The null-hypothesis (H_0) is that there will be no significant difference between the proportions of patients achieving metabolic control in the intervention group and the control group. The alternative hypothesis (H_1) is that there will be significantly more patients achieving metabolic control in the intervention group. For the purpose of this study, metabolic control is defined as a fasting glucose < 7.6 mmol/l and an HbA1c below a target stratified for three groups according to HbA1c at baseline: HbA1c $> 14\% \rightarrow$ target $< 10\%$; HbA1c $< 14\%$ and $> 10\% \rightarrow$ target $< 8\%$; HbA1c $< 10\% \rightarrow$ target $< 7.5\%$.

Determination of Sample Size

The aim of this study is to assess whether bicycle exercise followed by an intensive life style intervention can sufficiently restore metabolic control without anti-diabetic drugs as compared to a standard care control group.

Based on our clinical experience we assume that 80 % in the intervention group will reach the primary endpoint of metabolic control with no anti-diabetic drugs compared to only 40 % in the standard care control group.

A publication by Martinus et al.²¹ on adherence to a study sport program for newly diagnosed type 2 diabetes mellitus patients, shows up to 80 % adherence for the group that was additionally supported by a psychologist for increased motivation. The adherence to the program was significantly better in the group with support by the psychologist, as were the results regarding improvement of physiological parameters such as body mass, fat mass or strength.

A review on the effect of physical exercise on glycemic control found an average decrease of HbA1c by 0.6 mmol/l through exercise²² in diabetes patients at least one year after diagnosis and with a moderate hemoglobin elevation. Based on this data, our target ranges were extrapolated for patients with new-onset diabetes and higher HbA1c.

The inclusion of 28 patients per group (n total 62 patients including 10 % lost to follow-up) will provide 80 % power at an alpha level of 0.05. A number of 15 to 25 patients per center is envisaged.

Statistical Criteria of Termination of Trial

There will be no statistical criteria to terminate the trial early.

Planned Analyses

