4.2 Primary Objective

The primary objective is to investigate whether an intensive lifestyle intervention in untreated type 2 diabetes can adequately lower blood glucose and HbA1c levels compared to conventional standard of care anti-diabetic treatment.

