8.1.2 Control Intervention (Standard Treatment)

Standard therapy for type 2 diabetes usually consists of a variation of oral anti-diabetic medication and/or s. c. insulin therapy as well as a limited lifestyle intervention according to national and international guidelines (American Diabetes 2018)¹².

Administration of Experimental and Control Interventions

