8.1.4 Control Intervention

The control arm for this study will receive standard type 2 diabetes treatment after study enrollment. This treatment usually consists of a limited lifestyle intervention and oral anti-diabetic medication (i.e. Metformin, SGLT2-inhibitors, DPP-Inhibitors, GLP-1-receptor agonists etc.) or insulin therapy.

Dose/Device Modifications

Therapy for the participants of the intervention group has to be reassessed if:

- glucose values remain elevated above 15 mmol/l for more than 7 consecutive days
- in case of symptomatic hyperglycemia or re-hospitalization

In these cases, standard of care according to national and international guidelines will be implemented.

Compliance with Study Intervention

Patients in the intervention arm will be motivated by a specially trained psychologist and provided with an actigraph to monitor daily step count, overall physical activity and the scheduled training sessions. Personal motivation for the training sessions will be supported through telephone interviews, during study visits and with continuous self-evaluation. If the bicycle exercise is not completed or completed partly, this will be documented in the CRF.

Data Collection and Follow-up for Withdrawn Participants

Participants may withdraw or be withdrawn at any time. Subjects who discontinue participation will not be replaced. Withdrawal will be documented in the database with all other study data. All gathered data and samples until withdrawal of informed consent will be used anonymously for analysis. Follow-up will not take place if the patient has withdrawn informed consent, in all other cases follow-up will take place as planned.

Trial-specific Preventive Measures

Participants of the bicycle and intensive lifestyle modification group will, in addition to the general clinical visits, be closely monitored and coached with weekly telephone calls, thereby ensuring appropriate glucose management. If needed, standard of care medical treatment will be initiated also in the interventional group. All patient specific data will be recorded in an electronic case report form (eCRF).

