Patients who were randomized into the intervention group will be instructed in correct self-measurement of blood glucose by a member of the study team at study enrollment or on visit 2. They will receive a blood glucose monitor to document fasting glucose every morning during the first week of the study. This way the study team is able to supervise the metabolic situation and may start rescue medication if needed.

Concomitant Interventions (Treatments)

Permitted concomitant treatments are all medication the patient has taken prior to the initial visit. We expect no influence on the study by treatment of other diseases. Not permitted are any oral anti-diabetic drugs (except for Metformin) or Insulin for the intervention group, except in case it needs to be administered as rescue medication.

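### With the drug-free endpoint wording, standard care itself pushes controls towards failure, so a significant primary test need not mean better glycaemia, and the assumed 40% control rate is unsupported

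*Protocol*

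**What the plan says.** **Endpoint behind the sample size.** Section 11 (Determination of Sample Size) puts the intervention rate at 80% for this outcome: "primary endpoint of metabolic control with no anti-diabetic drugs compared to only 40 % in the standard care control group". The basis given is clinical experience. The synopsis also makes absence of anti-diabetic medication at 3 months part of the primary endpoint.

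**Endpoint elsewhere.** Section 5.1 and the definition under the hypothesis in section 11 use fasting glucose and stratified HbA1c targets. Neither contains a drug-free condition.

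**Control arm.** Section 8.1.2: "Standard therapy for type 2 diabetes usually consists of a variation of oral anti-diabetic medication", and/or insulin. Section 8.1.4: "This treatment usually consists of a limited lifestyle intervention and oral anti-diabetic medication", or insulin. Table 2 marks the start of Metformin in controls as optional. No expected share of controls on drugs is given.

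**Intervention arm.** Section 8 (Concomitant Interventions): "Not permitted are any oral anti-diabetic drugs (except for Metformin) or Insulin for the intervention group", with an exception for rescue medication. Sections 8.1.1 and 8.1.3 foresee Metformin from 3 months after enrolment. Section 8 also provides for standard-of-care drug treatment in this arm if needed.

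**Objective.** Section 4.2 asks whether the intervention can "adequately lower blood glucose and HbA1c levels compared to conventional standard of care anti-diabetic treatment".

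**Other outcomes.** Section 5.2 lists HbA1c change versus control at 6 and 12 months, and absolute HbA1c reduction per baseline group with no time point or comparator. It also lists target attainment per baseline group at 3 and 6 months without drugs other than Metformin. It lists no between-arm comparison at 3 months of target attainment regardless of drugs.

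**The concern.** The drug-free composite has two parts: being on target and being off drugs. The treatment policy of each arm largely settles the second part. A well-controlled control patient on a drug counts as a failure, while an equally well-controlled intervention patient without drugs counts as a success. The two arms can therefore differ on the composite when their glycaemia is the same.

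Two things follow. The 40% control rate implies something about drug use in standard care that the protocol neither states nor supports. And a significant primary result would not answer objective 4.2, which is a glycaemic comparison with drug treatment. In an open-label trial analysed by the investigators, the conclusion that the composite allows should be fixed before the data are seen.

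**Working it through.** **Inputs from the protocol.** 80% vs 40%, two-sided alpha 0.05, 80% power, 28 per group, 62 in total with 10% loss (section 11); Fisher's exact test (11.1.2); 1:1 allocation (6.1.1).

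**Inputs assumed, because the protocol gives none.** *q*, the share of controls on anti-diabetic drugs at day 90; *g*, the on-target rate, taken as equal in both arms and unrelated to drug use among controls; *r*, the share of the intervention arm that fails through rescue drugs.

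**1. The plan's own figure.** The two-proportion formula with continuity correction gives 28 per arm for 80% vs 40%. Exact Fisher power at 28 per arm, by full enumeration, is 0.823. For loss, 56 × 1.1 = 61.6, rounded up to 62. The stated size reproduces, so the issue lies in the input and its meaning, not in the arithmetic.

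**2. What 40% implies.** Control success = (1 − *q*) × (success rate among untreated controls). Since the second factor is at most 1, 40% requires 1 − *q* ≥ 0.40.
- 40% untreated: 0.40 / 0.40 = 100% of them must be on target.
- 50% untreated: 0.40 / 0.50 = 80%.
- 60% untreated: 0.40 / 0.60 = two thirds.

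**3. Equal glycaemia, *g* = 60% in both arms.** Control rate = 0.60 × (1 − *q*); intervention rate = 0.60 × (1 − *r*), which is 0.60 at *r* = 0 and 0.48 at *r* = 20%. Entries are exact probabilities, at 28 per arm, that Fisher's test is significant in favour of the intervention.

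| Controls on drugs (*q*) | Control rate | *r* = 0 | *r* = 20% |
|---|---|---|---|
| 40% | 0.36 | 0.32 | 0.09 |
| 50% | 0.30 | 0.51 | 0.20 |
| 60% | 0.24 | 0.71 | 0.37 |
| 75% | 0.15 | 0.93 | 0.70 |
| 80% | 0.12 | 0.96 | 0.80 |

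With *q* = 0 and *r* = 0 the corresponding probability is 0.013.

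**4. The planned effect from drug use alone.** With *g* = 80% in both arms, *q* = 50% and *r* = 0, the rates are 0.80 and 0.80 × 0.50 = 0.40. This is exactly the planned contrast, with power 0.823 and no glycaemic difference.

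**5. Effect on power.** Against 80%, exact power at 28 per arm is 0.956 if the control rate is 30% and 0.996 if it is 20%. A lower control rate raises power for the composite.

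**6. Precision of the missing comparison.** At 60% on target in both arms the 95% half-width is 1.96 × √(2 × 0.60 × 0.40 / 28) = 0.257, about 26 percentage points.

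**The case against.** **Control without drugs is a legitimate goal, and section 11 names it as the aim.** This stands. A proof-of-concept trial may test it, and no passage announces a claim of better glycaemia. What remains is the gap to objective 4.2, which the composite does not address.

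**The 40% is not shown to be wrong.** This also stands. A reader might infer that 40% contradicts sections 8.1.2 and 8.1.4, or that it needs every untreated control to be on target. The documents do not support either. Both sections say only that care usually includes drugs, Table 2 makes Metformin optional in controls, and universal success among untreated controls is needed only if exactly 40% are untreated. The figure is unsupported and sits awkwardly with the described care; it is not impossible.

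**The intervention arm is not strictly drug-free.** Correct. Rescue and standard-of-care treatment are allowed, and those patients also fail the composite. With 20% failing this way, the probabilities fall substantially, and at 40% of controls on drugs the figure is only 0.09.

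**Section 5.1 has no drug-free condition.** Under that wording treated controls can succeed and this issue disappears. The 80% vs 40% would then have been stated for a different endpoint from the one analysed.

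**Secondary outcomes already cover glycaemia.** Only in part. The 3-month outcome that allows Metformin still fails controls on any other drug or on insulin, and HbA1c change versus control is listed at 6 and 12 months only.

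**Conclusion.** The point holds for the drug-free wording in the synopsis and the sample-size section. Assignment drives one component of the endpoint. With equal glycaemia (60% on target in each arm), the test favours the intervention with probability 0.32 to 0.96 when 40 to 80% of controls are on drugs and no intervention patient is. With 20% rescue failures it is 0.37 to 0.80 when 60 to 80% of controls are on drugs. These figures rest on an assumed control drug share and on target attainment being unrelated to drug use among controls.

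A reader might also infer that the trial is underpowered. It is not: a control rate below 40% raises power for the composite. The harm is to interpretation, because a significant composite does not answer objective 4.2 and no listed 3-month comparison does so in its place. Nor is a win without glycaemic benefit certain: it depends on drug use in both arms, which the protocol does not quantify. This should be fixed, but it does not invalidate the design.

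**What to change.** Reconcile the endpoint wording across the synopsis, section 5.1 and section 11. If the drug-free condition is kept:

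1. **Section 11.1.2:** add, as a prespecified analysis alongside the primary test, the day-90 proportion on target regardless of drugs and the proportion off drugs, by arm, each with a risk difference and 95% confidence interval.
2. **Section 11.1.2, permitted conclusion:** state that a significant drug-free composite supports only that more patients were controlled without drugs. Any statement about glycaemic control versus standard care rests on the on-target difference and its interval. With a half-width of about 26 points, that comparison is descriptive and cannot by itself establish adequacy.
3. **Section 11, Determination of Sample Size:** state the control drug-use share and the success rate among untreated controls that together give the assumed 40%. This makes the assumption visible; it need not change the sample size.

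The cost is wording and one small table. HbA1c and medication are already scheduled at day 90 in both arms, so no extra visits or patients are needed. The price is a narrower permitted conclusion.
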